9. STUDY PROCEDURES

Recruitment for this trial will begin following receipt of all regulatory and ethics committee approvals and will conclude when 12 subjects have completed the 6-week visit.

When the site pharmacist is notified that the subject is available for device placement, the unblinded pharmacist will withdraw a device package from the refrigerator. The principle investigator will prepare the experimental device by cutting or shaping to fit the subject's cranial defect. The experimental device will be wetted, then placed into the defect in the same manner as placing an autologous bone graft, taking care to fit the device to the margins of the defect in all dimensions. The experimental site may or may not be covered with a vicryl screen for tissue support, and the wound will be closed by conventional means.

The preliminary safety assessment will be available approximately four months after enrollment has been completed. Follow-up of subjects will continue through two years.

Source documents will include subject diary cards, subject medical charts, telephone contact records, reports from clinical laboratory tests, and analytical results from tests conducted on clinical samples by Agenta and its contractors. Results of in-clinic assessments, as well as AE and SAE information, will be recorded directly onto

protocol Case Report Forms (CRFs) or will be transferred from source documents onto CRFs. Results of tests on clinical samples will be transferred directly from the source documents into the study database.

9.1 Study Visits

Screening Visit (Day -21 to -1)

Participants will be screened for eligibility to participate in the study. The following procedures must be performed during the screening period:

- a. Obtain Informed Consent prior to any study procedures.
- b. Check eligibility criteria.
- c. Obtain medical history.
- d. Record concomitant medication
- e. Perform physical examination.
- f. Obtain blood samples (10 mL + 5 mL) for screening clinical laboratory assessments.
- g. Obtain a blood sample (4 mL) for HIV serology and illicit drug screen.
- h. Obtain CT image of cranial defect.

Visit 1 (Day 0, Baseline)

- a. Confirm that the subject wishes to remain in the trial.
- i. Confirm eligibility criteria as needed.
- j. Obtain interim medical history as needed.
- k. Record concomitant medication as needed.
- l. Perform physical assessment as needed.
- m. Obtain blood samples (10 mL + 5 mL) and urine sample for clinical laboratory assessments if more than 3 days since prior screening.
- n. Obtain blood sample (4 mL) for PT and PTT tests if more than 3 days since prior screening.
- o. Administer experimental device.
- p. Keep the subject under observation for 30 minutes post administration and record any reaction in the source documents and CRF.
- q. Give participant the diary card with instructions for use.
- r. Record AEs and SAEs.
- s. Set up appointment for Visit 2 (Day 3).

Contact 1 (Day 1)

- a. Record symptoms and symptom severity on Telephone Contact Symptom Assessment Form.
- b. Record AEs and SAEs.
- c. Schedule in-clinic evaluation for moderate or severe AEs or SAEs, as clinically appropriate.

Contact 2 (Day 2)

- a. Record symptoms and symptom severity on Telephone Contact Symptom Assessment Form (Appendix D).
- b. Record AEs and SAEs.
- c. Schedule in-clinic evaluation for moderate or severe AEs or SAEs, as clinically appropriate.

Visit 2 (Day 3)

- a. Confirm that the subject wishes to remain in the trial.
- b. Obtain interim medical history.
- c. Review diary card with subject.
- d. Record concomitant medication.
- e. Perform physical assessment (vital signs, lymph node exam, and symptom directed exam).
- f. Record AEs and SAEs.
- g. Set up appointment for Visit 3 (Day 7).

Visit 3 (Day 7)

- a. Confirm that the subject wishes to remain in the trial.
- b. Obtain interim medical history.
- c. Record concomitant medication.

- d. Perform physical assessment (vital signs, lymph node exam, and symptom directed exam).
- e. Obtain blood samples (10 mL + 5 mL) and urine sample for clinical laboratory assessments.
- f. Obtain blood sample (4 mL) for PT and PTT tests.
- g. Collect and discuss diary card / distribute new diary card.
- h. Record AEs and SAEs.
- i. Set up appointment for Visit 4 (Day 42).

Visit 4 (Day 42)

- a. Confirm that the subject wishes to remain in the trial.
- b. Obtain interim medical history.
- c. Review diary card with subject.
- d. Record concomitant medication.
- e. Perform physical assessment (vital signs, lymph node exam, and symptom directed exam).
- f. Obtain blood samples (10 mL + 5 mL) and urine sample for clinical laboratory assessments.
- g. Obtain blood sample (4 mL) for PT and PTT tests.
- h. Record AEs and SAEs.
- i. Obtain radiographs and CT images of experimentally treated cranial defect.
- j. Set up appointment for Visit 5 (Day 180).

Visit 5 (Day 180)

- a. Confirm that the subject wishes to remain in the trial.
- b. Obtain interim medical history.
- c. Review diary card with subject.
- d. Record concomitant medication.
- e. Perform physical assessment (vital signs, lymph node exam, and symptom directed exam).
- f. Record AEs and SAEs.
- g. Obtain CT images of experimentally treated cranial defect.
- h. Set up appointment for Visit 6 (Day 360).

Visit 6 (Day 360)

- a. Confirm that the subject wishes to remain in the trial.
- b. Obtain interim medical history.
- c. Review diary card with subject.
- d. Record concomitant medication.
- e. Perform physical assessment (vital signs, lymph node exam, and symptom directed exam).
- f. Record AEs and SAEs.
- g. Obtain CT images of experimentally treated cranial defect.
- h. Set up appointment for Contact 3 (Day 730).

Telephone Follow-up (Day 730)

Study personnel (study coordinator or other personnel assigned by the investigator) will contact the participant to collect information on ongoing, previously recorded adverse events and new or ongoing SAEs. Reminder postcards will be mailed to each participant approximately one month prior to this contact. Study personnel will contact the participant by telephone approximately two weeks in advance of the follow-up target date to schedule a time for the telephone contact. During the telephone conversation, study personnel will collect interim medical history as well as update contact information.

Contact 3 (Day 730)

- a. Confirm that the subject wishes to remain in the trial.
- b. Obtain interim medical history.
- c. Record AEs and SAEs.
- d. Verify telephone contact information and mailing address and provide instructions to participant in the event of a change in contact information.

Additional Clinic Visits

Any subject with an abnormal laboratory result or who experiences an adverse event may be requested to come into the clinic for additional follow-up evaluation not specified by the protocol if this is deemed medically prudent by the investigator.

9.2 *Obtaining, Handling, Storage, and Shipment of Specimens*

9.2.1 *Blood Samples for Safety Laboratory Tests*

Blood samples collected for safety analysis will be labeled and handled per the local reference laboratory standard operating procedures for hematology and biochemistry profiles. Blood samples for safety laboratory tests will include one 5 mL and one 10 mL sample, as well as one 4 mL sample for PT and PTT testing where specified.

9.2.2 *Urine Samples*

A clean-catch urine sample will be collected by each participant for safety evaluation. Study personnel will be responsible for instructing subjects on this technique. Urine samples will be handled and labeled per the local reference laboratory standard operating procedures for urinalysis.

9.3 *Safety Data Review*

The SRC will perform a review of the safety data through seven days post-administration for the first three subjects, and through seven days post-administration for all subsequent subjects. The SRC will use the following evaluation criteria to approve the completion of enrollment after the first 3 subjects:

- a) Absence of SAEs or severe AEs "definitely", "probably" or "possibly" related to the experimental device.
- b) No evidence of severe hematologic or biochemical toxicity.
- c) No consistent pattern of AEs that, in the judgment of the SRC, represents a significant threat to the safety of the subjects with continued enrollment.

Approval from Agenta will be obtained before proceeding with treatment of subjects 4-12.

9.4 *Compliance with Protocol*

All participants who receive the experimental device will be included in the safety evaluation.

The following events are to be considered sufficient reason for discontinuation of a participant from the study:

1. Poor or non-compliance with visit schedule. In cases where a participant is outside the recommended visit schedule, the participant may be continued in the study as a protocol violator and will be analyzed as such as long as the study personnel receives approval from both Agenta and the Principal Investigator.
2. Any situation where, in the opinion of the investigator, continuation of the study would not be in the best interest of the participant, including, but not limited to, illness requiring immunosuppressive therapy.
3. Individual request of the study participant.
4. Decision of Agenta.

The collection of adverse events including subject diaries, in-clinic assessments, and the 6, 12, and 24 month evaluations will continue for subjects who are discontinued but agree to continue study follow up.

In the case of participants who fail to appear for a follow-up visit or are not able to be contacted by telephone, extensive effort (i.e. documented telephone calls and certified mail) should be undertaken to locate or re-call them to determine their health status. These efforts must be documented in the participant's record.

If a certified letter is sent to an unresponsive participant and then returned to the study site unopened, or if the letter is received and signed for but the participant cannot be contacted, the returned certified letter or receipt must be stored with the participant's records. These subjects will be terminated from the trial and their data will be analyzed as "lost to follow-up."

Subjects who fail to complete the study or withdraw for any reason prior to completion of the day 42 visit and examination will be replaced with new enrollment if feasible.

All subjects will be classified at the end of the trial according to the following design:

1. Subjects who complete all the visits according to the protocol through Day 180 will be classified as normal study completion.
2. Subjects who receive the study device but missed study visits or had visits performed outside the protocol windows will be classified as study completion not according to protocol.
3. Any participant that is withdrawn from the study at any time either at the discretion of the Investigator or Agenta will be classified as "withdrawal."
4. Any participant that requests to be withdrawn will be classified as "drop-out." The reason for this must be clearly documented in the participant's record.
5. Any participant that does not finish the trial and with whom the study staff is unable to make contact after extensive effort will be classified as "lost to follow-up."

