11.1.4 Adverse Event Grading Scales

The severity of all adverse events will be graded as mild (Grade 1), moderate (Grade 2), severe (Grade 3), or potentially life threatening (Grade 4) according to the adverse event grading scale provided below. This grading scale will be used for local adverse events (those related to the cranial site of device administration) and systemic adverse events.

Mild (Grade 1)	Moderate (Grade 2)	Severe (Grade 3)	Potentially Life Threatening (Grade 4)
Symptom is present but does not interfere with activity	Symptom interferes with some activities but does not cause missed attendance at school or work	Incapacitating, unable to attend school or work or perform essential daily activities	Requires emergency room visit or hospitalization

Abnormal vital signs will be graded according to the above severity scale. This grading scale is based on the scale provided in the draft FDA guidance for industry, “Toxicity Grading Scale for Healthy Adult and Adolescent Volunteers Enrolled in Preventive Vaccine Clinical Trials” (April 2005).”

Any "severe" rating for local or systemic events requires the participant to call the study site for evaluation, the study site to notify the Medical Monitor (at the discretion of the investigator), and place comments on the AE page of the CRF that describe the event(s). Any severe adverse event that is deemed possibly, probably or definitely related to the study treatment will invoke a temporary stopping rule for the study to permit evaluation of the event by the SRC (see Section 14.3).

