14. SAFETY REVIEW COMMITTEE

The Safety Review Committee (SRC) will be established to review all safety data and make recommendations to Agenta regarding the continuation of the trial. This group may recommend trial continuation as scheduled, modifications to the current enrollment plan and/or cessation of device implantation.

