14.2 Meeting Schedule/ Adverse Event Review

The SRC will have a scheduled meeting at least once per week during the period of active enrollment and follow-up for each enrolled participant to 42 days. All members of the SRC will review the safety data weekly. Scheduled meetings may be cancelled at the agreement of all three SRC members if there are no safety issues to discuss. The SRC will hold a meeting to review the Day 7 data for the first 3 subjects, and the Day 7 safety data for each subject for the remaining 9 subjects. The SRC will recommend to either continue enrollment or termination of enrollment based on the safety and tolerability of the study product. All AEs that are moderate or mild will be submitted within 7 days from the site to the Study Medical Monitor. SAEs and severe adverse events will be reported within 24 hours after the clinical trial site is aware of the event.

The Medical Monitor will keep and maintain documentation for all SRC meetings with meeting minutes. Agenta personnel will tabulate the data for SRC review.

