14.3 Stopping Rules

Stopping rules will be in place to arrest the enrollment process and suspend all experimental device placement with the occurrence of significant safety event(s). The stopping rules are:

- Any SAE or severe AE that is definitely, probably, or possibly related to the experimental device in the opinion of the investigator or Safety Review Committee.
- Occurrence of 3 or more moderate AEs of the same type that are definitely, probably, or possibly related to the study agent in the opinion of the investigator or Safety Review Committee.

The occurrence of AEs and SAEs will be monitored by the Medical Monitor who will notify the other members of the SRC if a condition is met to institute a stop rule. Enrollment and study agent administration cannot continue after a stop rule has been implemented until the SRC has reviewed the AEs and other subject safety data and made a recommendation to continue the trial as planned, modify the protocol or stop enrollment. The recommendation of the SRC must be reviewed and approved by Agenta.

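### Severe laboratory toxicity bars enrolment after subject 3 (Protocol 9.3(b)) but is neither a 14.3 stopping rule nor a stated criterion for later Day 7 reviews, and the scale that grades it is ambiguous

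*Protocol*

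**What the plan says.** **The decision after subject 3.** Protocol 9.3 introduces its list with "The SRC will use the following evaluation criteria to approve the completion of enrollment after the first 3 subjects". Criterion (a) concerns related SAEs or severe AEs, (b) is "No evidence of severe hematologic or biochemical toxicity", and (c) concerns a worrying pattern of AEs. Criterion (b) requires neither AE status nor a judgement of relatedness.

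**The stopping rules.** Section 14.3 has two. The first is "Any SAE or severe AE that is definitely, probably, or possibly related to the experimental device in the opinion of the investigator" or of the SRC. The second is "Occurrence of 3 or more moderate AEs of the same type that are definitely, probably, or possibly related to the study agent", again in the opinion of either party. Neither names laboratory values.

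**How a laboratory value becomes an AE and is graded.** Under 11.1.5 an out-of-range value is an AE only if the investigator considers it clinically significant. Section 11.1.4 begins "The severity of all adverse events will be graded as mild (Grade 1), moderate (Grade 2), severe (Grade 3" and goes on to Grade 4. Grades 1 to 3 are defined by effect on activity, and Grade 4 by the need for an emergency room visit or hospitalization. Footnote 2 of the Schedule (section 3) instead has laboratory values evaluated under an FDA draft guidance that it does not name. Footnote 3 assumes laboratory severity grades exist, and 13.3.1 refers to toxicity criteria that it places in the protocol.

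**Continuing oversight.** Section 14.2 states "The SRC will have a scheduled meeting at least once per week during the period of active enrollment and follow-up for each enrolled participant"; that follow-up period ends at Day 42. It also requires review of each remaining subject's Day 7 data, and says "The SRC will recommend to either continue enrollment or termination of enrollment based on the safety and tolerability of the study product". Section 14 adds "This group may recommend trial continuation as scheduled, modifications to the current enrollment plan and/or cessation of device implantation".

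**The concern.** The protocol treats severe laboratory toxicity as sufficient reason not to proceed past subject 3. It does not say that the same finding in subject 5, or at Day 42 in any subject, pauses implants. After subject 3, such a finding reaches 14.3 only through the AE route, which depends on the investigator's view of clinical significance and on a severity grade whose scale is not settled.

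Section 5.5 says there is no previous human experience with this plasmid approach, and safety is the primary objective (6.1). The one-per-week limit on enrolment covers only the first three subjects (7.1), so further implants could go ahead while an abnormality waits for discussion. A low grade also slows escalation: under 14.2, severe AEs and SAEs are reported within 24 hours, while mild and moderate AEs may take 7 days to reach the Medical Monitor.

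**Working it through.** No figure in the plan bears on this point; the probabilities in 13.1 concern counts of SAEs. The check compares provisions and then counts draws.

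**1. What each provision requires**

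| | 9.3(b) | 14.3 |
|---|---|---|
| When it applies | Once, after subject 3 | Throughout |
| Must be recorded as an AE | No | Yes |
| Must be at least possibly related | No | Yes |
| Severity needed | Severe toxicity, no cut-off stated | SAE, severe AE, or 3 moderate AEs of the same type |

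**2. A test case (hypothetical value).** Take a symptom-free ALT of 450 U/L at Day 7. The male upper limit in Appendix A is 45, so this is 450 / 45 = 10 times the limit.

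- In subjects 1–3: if the SRC regards it as severe, 9.3(b) is not met.
- In subject 5, recorded as a possibly related AE, with 11.1.4 governing: Grade 3 needs incapacity, which is absent. Grade 4 needs emergency or hospital care, assumed absent here. Neither 14.3 rule is met unless the event is classed as an SAE, for instance as an important medical event under section 10.
- In subject 5, recorded as a possibly related AE, with the guidance in footnote 2 governing: if that guidance grades it severe, the first 14.3 rule applies. The protocol prints no cut-off, so this cannot be settled from the document.
- In subject 5, considered not clinically significant: it is not an AE, and 14.3 is not reached on either reading.

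**3. Laboratory cut-offs in the protocol.** Section 11.1.5 lists 11 haematology + 11 chemistry + 15 urinalysis = 37 tests. Appendix A, as shown, gives a critical limit for 8 of them: haematocrit, platelets, sodium, potassium, bicarbonate, glucose, calcium and urine protein. ALT is not among them. Mild, moderate and severe cut-offs are given for none.

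**4. Draws to which 9.3(b) attaches**

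- Scheduled post-implant draws: 12 subjects × 2 (Days 7 and 42) = 24. Section 11.1.5 says Days 3 and 42, but the count is the same.
- Under 9.3(b): the first draw of subjects 1–3 = 3.
- Outside it: 24 − 3 = 21, made up of 9 Day 7 draws and 12 Day 42 draws. All are still subject to SRC review.

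**5. Draws on which a pause could act.** A pause helps only if an implant is still to come. Without replacements, subject 12's two draws can pause nothing, so the ceiling is 24 − 2 = 22.

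Assume one implant per week throughout; the protocol sets a pace only for the first three. Subject 12 is then implanted on study day 7 × 11 = 77. Subject k's Day 42 draw falls on day 7(k − 1) + 42, which is before day 77 only for k ≤ 5. Faster accrual leaves fewer useful Day 42 draws, and slower accrual leaves more.

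**The case against.** **The SRC sees these data anyway.** It reviews safety weekly and reviews every later subject's Day 7 data, and it can recommend stopping implants. Criterion 9.3(b) is itself a judgement by the same committee without a threshold. This stands, and it narrows the point to the lack of a pre-stated laboratory trigger and automatic pause. It does not close the gap, because the later reviews have only a general safety and tolerability standard and a weekly meeting can be cancelled if all three members agree there is nothing to discuss.

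**Laboratory values may not be graded on 11.1.4 at all.** That section mentions local and systemic events and abnormal vital signs but not laboratory values, and the Schedule footnotes point to a separate guidance. This is a fair competing reading, so the grading issue is an ambiguity and not an established fault. Even on this reading, an abnormality not recorded as an AE stays outside 14.3. A severe toxicity considered clinically insignificant should, however, be rare.

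**A stricter check on the first few subjects is a legitimate choice.** Trauma and craniotomy patients may have abnormal laboratory values for reasons unrelated to the device. This also stands, and is why the proposed rule carries a relatedness condition that 9.3(b) lacks.

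**Stronger readings to avoid.** A reader might infer that any symptom-free laboratory abnormality is graded mild at most. Grade 4 contradicts this, because an abnormality needing emergency or hospital care qualifies whatever its effect on activity. A reader might also infer that no laboratory finding can trigger 14.3, but one recorded as a related SAE or severe AE does. Nor are the 21 draws outside 9.3(b) unreviewed.

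**Conclusion.** The concern holds in limited form. A criterion that the protocol treats as decisive after subject 3 is not carried into 14.3 or stated for the Day 7 reviews of subjects 4–12. If 11.1.4 governs grading, a symptom-free severe abnormality managed without emergency or hospital care, and not classed as an SAE, triggers no automatic pause. Whether 11.1.4 governs cannot be decided from the document.

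The size is descriptive: 9.3(b) attaches to 3 of 24 scheduled post-implant draws, and the other 21 rely on the AE route or SRC discretion. This is not a risk estimate; the protocol gives no rate of laboratory toxicity and none is assumed. It would also be wrong to infer that a new stopping rule protects someone on all 24 draws, since only draws taken before the last implant can matter. No sample-size or error-rate figure changes. This is a cheap safety improvement to a protocol that already provides continuing oversight.

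**What to change.** 1. Add a bullet to 14.3: severe haematologic or biochemical toxicity on any post-implant safety laboratory test, whether or not recorded as an AE, that is at least possibly device-related in the opinion of the investigator or SRC, suspends further implants until SRC review.
2. State in 11.1.4 that laboratory values are graded on a named laboratory scale with cut-offs, taking change from Day 0 into account, and not on the activity scale. The scale should suit post-craniotomy patients; the only guidance titled in 11.1.4 is for healthy vaccine volunteers.
3. State in 9.3 and 14.2 that criteria 9.3(a)–(c) apply to each later Day 7 review.

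The cost is one bullet, a sentence in each of three sections, and a grading table. The laboratory tests are already scheduled. The downside is a possible extra SRC review and a short enrolment pause, limited by the relatedness condition and the use of change from baseline.

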10.1 Recording of Adverse Events

Adverse events will be recorded for all subjects who receive the study device. Adverse events will be documented in subject diaries, during in-clinic assessments, and during telephone contacts through Contact 3 (Day 730) of the study. All adverse events will be graded by severity and relationship to the experimental device and followed until resolution or the completion of subject participation. All SAEs will be recorded throughout the 2 year period of safety surveillance.

Any subject who was discontinued due to an AE or non-adherence to the protocol windows for study agent administration will be followed for safety and efficacy endpoints by clinic visits, telephone contacts, and subject diaries as specified by the protocol. All safety evaluations will continue to be completed according to the protocol, if possible.

All AEs that are moderate or mild will be submitted within 7 days from the site to the designated Medical Monitor, [name].

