Participants will be instructed to call the study site to report SAEs at any time during the study period through 24 months. In addition, active surveillance of SAEs will be performed at every scheduled site visit or telephone call. In the event that a study participant reports a SAE, study personnel will be authorized to visit or telephone the participant until the problem is resolved. Any SAE is to be documented and fully described whether or not it is consider to be related to the study device.

A report of any SAE must be followed by a written report to the IRB, the SRC and to Agenta, by the Investigator, including a full description of the event and any sequelae. All deaths, whether considered device-related or not, must also be reported immediately to the IRB, the SRB, and to Agenta.

Agenta will report all SAEs to the government agencies, adhering to timelines for reporting outlined in Therapeutic Products Program Directorate Guidelines (ICH/GCP) and the Code of Federal Regulations (21CFR 312.32). The FDA will be notified of any SAE as soon as possible, not later than 15 days, and within 7 days for any death or life-threatening event associated with the drug substance (experimental device).

All SAEs must also be recorded in the appropriate section of the CRF. All reported SAEs will be reviewed periodically by the SRC.

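### Section 9.4 terminates a subject after one failed tracing round with no renewed contact planned, and keeps out-of-window subjects only by case-by-case approval without a criterion

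*Protocol*

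**What the plan says.** **Unreachable subjects.** Section 9.4 begins: "In the case of participants who fail to appear for a follow-up visit or are not able to be contacted by telephone, extensive effort" must be made to trace them, by documented telephone calls and certified mail. Two outcomes of the letter lead to termination. One is that it never gets opened: "If a certified letter is sent to an unresponsive participant and then returned to the study site unopened". The second is delivery with no reply that leads anywhere: "or if the letter is received and signed for but the participant cannot be contacted". For both outcomes the consequence is the same: "These subjects will be terminated from the trial and their data will be analyzed as" lost to follow-up. The list of end-of-trial classes in the same section repeats that extensive effort must come first. Neither place mentions another attempt at a later visit or at the two-year call.

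**Late or missed visits.** The first sufficient reason for discontinuation in section 9.4 is "Poor or non-compliance with visit schedule". A subject outside the schedule is not necessarily removed. The wording is: "participant may be continued in the study as a protocol violator and will be analyzed as such as long as the study personnel receives". What has to be obtained is the joint agreement of sponsor and Principal Investigator. No ground for giving or refusing approval is stated.

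**What the protocol promises.** Section 10.1: "All SAEs will be recorded throughout the 2 year period of safety surveillance". Section 10.2: "active surveillance of SAEs will be performed at every scheduled site visit or telephone call". Section 7.1 likewise has SAEs collected over the full two years.

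**What limits the problem.** Section 9.4 continues adverse event collection, with diaries, in-clinic assessments and the 6, 12 and 24 month evaluations, for discontinued subjects who agree. It keeps every device recipient in the safety evaluation. It has a completion class for subjects with missed or out-of-window visits. It replaces subjects lost before completing Day 42, if feasible.

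**The concern.** Safety is the primary objective, and section 5.5 states that there is no previous human experience with this plasmid approach. The implant stays in place whether or not contact continues. A person who does not answer around one visit may be ill or admitted elsewhere, so these are the subjects in whom later events most need to be found. A rule that closes the file after one tracing round gives up the chance of reaching them six or twelve months later.

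The approval condition raises a different issue. Sponsor and investigator both know the treatment and the results so far, and section 13.1.1 puts the analysis under the sponsor's control. A case-by-case decision with no criterion can, without any intent, favour subjects who are doing well. With 12 subjects, each is 1/12 = 8.3% of the denominator.

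**Working it through.** **1. Which clause covers whom**

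| Situation | Rule in 9.4 | Does follow-up continue? |
|---|---|---|
| Visit missed, subject then reached | May be classed as completing, but not according to protocol | Yes |
| Visit late, approval given | Continued as a protocol violator | Yes |
| Visit late, approval not given | Discontinued | Safety follow-up yes, if the subject agrees; CT not clearly covered |
| Not reached after calls and certified letter | Terminated, lost to follow-up | No later attempt stated; consent to continue cannot be obtained |

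The third row is unclear on CT because the continuation clause in 9.4 is about adverse event collection and does not name imaging. Section 10.1 does extend follow-up to efficacy endpoints, but for subjects discontinued because of an adverse event or because of windows for administering the study agent. There is one implantation, on Day 0, so that wording does not plainly cover a late follow-up visit.

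**2. When a visit counts as late**

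The Schedule of Evaluations gives Day 42 +/- 4. Section 13.2.1 gives Day 42 +/- 7 for imaging. A visit on Day 47 is 47 - 42 = 5 days late: outside the first window and inside the second. For Day 180 the two places give +/- 28 and +/- 14. The trigger for the approval rule is therefore itself unsettled.

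**3. Surveillance time after termination**

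Using Day 720 from the Schedule of Evaluations:
- terminated at Day 42: (720 - 42)/720 = 678/720 = 94.2% remaining, three scheduled contacts (Days 180, 360, 720)
- terminated at Day 180: (720 - 180)/720 = 540/720 = 75.0% remaining, two scheduled contacts
- terminated at Day 360: (720 - 360)/720 = 360/720 = 50.0% remaining, one scheduled contact

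A subject lost before completing Day 42 is replaced if feasible. That restores the count but not that person's surveillance.

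**4. Effect on what the trial can detect**

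Section 13.1 states a 90% chance of at least one SAE among 10 subjects at a true rate of 21%. Check: 1 - (1 - 0.21)^10 = 1 - 0.79^10 = 0.905, so the figure reproduces.

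The protocol gives no dropout rate, so a range is shown. For n subjects followed:
- chance of at least one SAE at a 21% rate: 1 - 0.79^n
- smallest rate seen with 90% probability: 1 - 0.1^(1/n)
- one-sided 95% upper bound if no event is seen: 1 - 0.05^(1/n)

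| n followed | Chance at 21% | Smallest rate for 90% | Upper bound, zero events |
|---|---|---|---|
| 12 | 94.1% | 17.5% | 22.1% |
| 11 | 92.5% | 18.9% | 23.8% |
| 10 | 90.5% | 20.6% | 25.9% |
| 9 | 88.0% | 22.6% | 28.3% |
| 8 | 84.8% | 25.0% | 31.2% |
| 6 | 75.7% | 31.9% | 39.3% |

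The planned 12 leaves a margin of two subjects over the 10 used in section 13.1. A third complete loss takes the chance below the stated 90%.

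**The case against.** Three stronger readings are tempting, and the protocol supports none of them.

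- *One unanswered visit ends participation.* It does not. Calls and certified mail must come first, and a missed visit alone is compatible with completion. What stands is that one unsuccessful round, at any single visit, is enough, and that no retry is planned.
- *A late visit ends surveillance unless the sponsor agrees.* Approval is joint with the Principal Investigator, and a discontinued subject who agrees keeps adverse event follow-up to 24 months. There is no contradiction with sections 10.1 and 10.2 here. What stands is the missing criterion and the uncertain position of the later CT scans.
- *Losses shrink the safety denominator.* All device recipients stay in the safety evaluation, and events before the loss count. The denominator is fixed, but events after the loss may still go unseen.

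On the unreachable subjects, one can also say that section 10.1 continues evaluations where possible and that section 10.2 asks participants to report SAEs themselves through 24 months. So this is a gap in the wording more than a flat contradiction. But self-reporting is passive, and section 10.2 itself promises active surveillance at every scheduled contact. A site that follows 9.4 literally has no instruction to try again.

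Section 9.4 also lists a sponsor decision as a separate discontinuation reason. Removing the approval condition would narrow sponsor discretion but not end it.

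**Conclusion.** The point holds in two limited parts. First, following 9.4 as written can cut short the two-year surveillance of any subject not reached in one tracing round, and no other clause recovers that subject. Second, whether an out-of-window subject stays in the study proper, and probably whether CT follow-up continues, depends on an unblinded joint decision with no criterion. An exit before Day 42 is completed can also change who makes up the 12, because section 9 recruits until 12 subjects have completed the 6-week visit.

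The move from 22.1% to 28.3% and the fall to 88.0% illustrate a worst case. They assume three losses, none replaced, each contributing no information. With two such losses the stated 90% is still met. The case for the change rests on its very low cost in a first-in-human safety trial, not on a predicted number of losses.

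**What to change.** In section 9.4:

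1. Replace termination after failed tracing with this rule: record the visit as missed, repeat the contact attempt at each remaining scheduled timepoint, and assign loss to follow-up only when the two-year contact window closes without contact. The protocol gives that contact as both Day 720 and Day 730, and the two must be reconciled.
2. Make continued follow-up, including CT, the default after a missed or out-of-window visit, unless the subject withdraws or the investigator judges imaging not to be in the subject's interest (section 11.2 already provides for this). Record the visit as a deviation, in line with the existing completion class for such subjects.
3. Remove visit-schedule non-compliance as a discontinuation reason, together with the approval condition.
4. Reconcile the Day 42 and Day 180 windows between the Schedule of Evaluations and section 13.2.1, so that it is clear which visits are deviations.

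The cost is an amendment of wording and a few extra contact attempts by existing staff for at most the small number of subjects enrolled. No procedure is added to the schedule.
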